 - In a Sentinel feasibility assessment of identified health plan members meeting similar inclusion and exclusion criteria as this trial, 33% had evidence of OAC initiation in a 1 year period of follow-up.
- 38% OAC initiation rate in the early intervention arm (a 5% absolute improvement in OAC initiation over the 33% OA initiation expected in the delayed intervention arm over 1-year follow-up)
- 1-year attrition rate: 30% dropout or lost-to-follow-up
- Two-sided type I error of 0.05
- Roughly 10,000 patients (Table below) will yield more than 99% power to detect a 5% absolute difference

[figure not shown]

Power	Total sample size (2-arm)	Early Intervention	Delayed Intervention
90%	5610	2805	2805
95%	6910	3455	3455
99%	9718	4859	4859

Total Number of Patients in a 2-arm study (Unadjusted for dropouts)

OAC Initiation Endpoint (33% Control Rate), continuity corrected Chi-square

2. Important Secondary Analysis of Stroke or TIA

A study with approximately 80,000 patients is well powered for the outcome of stroke or TIA over the course of the follow-up through the date on which at least 80% of eligible study participants have at least 12 months of follow-up time, under certain assumptions listed below:

- 1-year stroke or TIA rate: 18% among patients not treated with OAC
- 1-year stroke or TIA rate: 7% among patients treated with at least 1 OAC fill
- Duration of follow-up: 1 year
- 33% of delayed intervention patients will have at least 1 fill of OAC, meaning the 1 year stroke or TIA rate in the delayed intervention group would be 14.4%
- If 38% of early intervention patients have at least 1 fill of OAC (meaning the 1 year stroke or TIA rate in the early intervention group would be 13.82%, i.e., an absolute reduction of 0.55%), the study will have 46% power to detect this 0.55% reduction. However, if 40.5% of early intervention patients have at least 1 fill of OAC (meaning the 1 year stroke or TIA rate in the early intervention group would be 13.54%, i.e., an absolute reduction of 0.83%), the study will have 80% power to detect this 0.83% reduction.

- 1-year attrition rate: 30% dropout or lost-to-follow-up
- Two-sided type I error of 0.05

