1. 33% OAC initiation rate in the delayed intervention arm
2. 38% OAC initiation rate in the early intervention arm (5% absolute improvement in OAC initiation over the 33% OAC initiation expected in the delayed intervention arm over 1-year follow-up)
3. 1-year attrition rate: 30% dropout or lost-to-follow-up
4. Two-sided type I error rate of 0.05
5. Roughly 10,000 patients who meet the inclusion/exclusion criteria will yield more than 99% power to detect a 5% absolute difference

Power	Total sample size (2-arm)	Early Intervention	Delayed Intervention
90%	5610	2805	2805
95%	6910	3455	3455
99%	9718	4859	4859

2. Important Secondary Outcome of Stroke or TIA

A study with approximately 80,000 patients could provide reasonable power for stroke or TIA outcome under certain assumptions listed below:

- 1-year stroke or TIA rate: 18% among patients not treated with OAC
- 1-year stroke or TIA rate: 7% among patients treated with at least 1 OAC fill
- Duration of follow-up: 1 year
- 33% of delayed intervention patients will have at least 1 fill of OAC, meaning the 1-year stroke or TIA rate in the delayed intervention group would be 14.4%
- 1-year attrition rate: 30% dropout or lost-to-follow-up
- Two-sided type I error of 0.05
- If 38% of early intervention patients have at least 1 fill of OAC (meaning the 1-year stroke or TIA rate in the early intervention group would be 13.82%, i.e., an absolute reduction of 0.55%), the study will have 46% power to detect this 0.55% reduction. However, if 40.5% of early intervention patients have at least 1 fill of OAC (meaning the 1-year stroke or TIA rate in the

early intervention group would be 13.54%, i.e., an absolute reduction of 0.83%), the study will have 80% power to detect this 0.83% reduction.

8. The sample size has 80% power to detect a 0.5% absolute reduction in stroke, assuming a cumulative 1-year incidence of stroke of 4.2% in control (delayed intervention arm) patients and 3.7% in intervention (early intervention arm) patients. The assumption is that patients not on oral anticoagulation have an annual stroke rate of 5%, and stroke will be reduced by 50% (HR=0.5) in the treated (anticoagulated) population. The 80% power requires that 52% of early intervention arm patients are treated at 1-year as compared to 33% in the control arm.

II. STATISTICAL ANALYSIS

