All possible person-time will be used to assess participants’ outcomes. For the time-to-event analysis, patients will be censored from the analysis at the time of death, disenrollment from the health plan, loss of medical or pharmacy coverage, or change in eligibility for inclusion in research based on health plan membership.

[figure not shown]
Providers may have more than 1 patient in the study – either within the same arm or in both the early and delayed intervention arms. The frequency of this, when provider overlap can be identified, will be reported descriptively and it is expected to be a low proportion of whole population. Depending on the number of patients in this scenario, a sensitivity analysis may be considered to examine the effect.

There were a few variations in the implementation of the early intervention across the Data Partners due to pragmatic issues. The intervention per the protocol is targeted at both member and provider (i.e., the provider who gave most recent AF diagnosis). If the AF provider was a facility in the source data, the educational intervention was applied to the member only, unless the site chose an alternate provider. In the latter case, the intervention was sent to both the member and the alternate provider. The number of patients in each of these variations to the intended intervention will be reported.

A detailed Consort flow diagram will be provided showing the number of patients randomized to the early and delayed intervention groups, the numbers of subjects lost to follow up or excluded from analyses, and the number of subjects evaluable for the key study endpoints (Figure 1).¹

All analyses will be conducted using SAS version 9.4 or higher software (SAS Institute Inc., Cary, NC). However, version and modules to be used could vary from one Data Partner to another. All tests will be two-sided and a p-value of <0.05 will be considered statistically significant. No multiplicity adjustment will be made.

Figure 1. Consort Flow Diagram

A. METHODS FOR ANALYSIS IN DISTRIBUTED DATA NETWORKS

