OAC dispensing or first of 4 INRs at 42 days							
OAC dispensing or first of 4 INRs at 90 days							
OAC dispensing or first of 4 INRs at 183 days							

Table 2c. Odds ratio of filling at least one OAC dispensing or 4 or more INRs (primary endpoint) over the course of the 12-months of follow-up: early intervention vs. delayed intervention, by age, sex, and CHADS-VASC score in the modified intention to treat (mITT) analysis

	Early Intervention, n/N (%)	Delayed Intervention, n/N (%)	Unadj. Parameter Estimate (SE)	Unadj. Odd Ratio (95% CI)	Adj. Parameter Estimate (SE)	Adj. Odds Ratio (95% CI)	p-value for adjusted OR
OAC dispensing or first of 4 INRs – by sex							
Female							
Male							
OAC dispensing or first of 4 INRs – by age							
≤64 yrs							
65-74 yrs							
75-84 yrs							
≥85 yrs							
OAC dispensing or first of 4 INRs – by CHADS-VASC							
2-3							
4-5							
≥6							

Table 3. Hazard ratio of at least one OAC dispensing or 4 or more INRs (primary endpoint) at 12 months: early intervention vs. delayed intervention in the modified intention to treat (mITT) analysis

	Early Intervention, Cumulative incidence (95% CI)	Delayed Intervention, Cumulative incidence (95% CI)	Parameter Estimate (SE)	Hazard Ratio (95% CI)	p-value
OAC dispensing or first of 4 INRs at 365 days					
Met endpoint due to OAC					
Met endpoint due to 4 INRs					
Met due to 4 INR test PX codes (CPT)					
Met endpoint due to other code					

Kaplan Meier curves will be generated for analyses related to Table 3.

Table 4. Numbers and proportions of filling at least one OAC dispensing or 4 or more INRs (primary endpoint) over the course of the 12-months of follow-up in intervention arm: patients with provider letter vs. patients without provider letter in the modified intention to treat (mITT) analysis

	Patients with Provider Letter, n/N (%)	Patients without Provider Letter, n/N (%)	p-value
OAC dispensing or 4 INRs at 365 days			

Table 5. Proportion of days on an OAC during all follow up time, among those treated for at least 1 day: early intervention vs. delayed intervention in the modified intention to treat (mITT) analysis

	Early Intervention	Delayed Intervention	p-value
Total number			
Number of days on an OAC			
Mean (SD)			
Median			
Minimum			
25 th percentile			
75 th percentile			
Maximum			
Number of OAC dispensings			
Mean (SD)			
Median (Min, 25 th , 75 th , Max)			
Minimum			

25 th percentile			
75 th percentile			
Maximum			

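### SAP Table 2c plans nine within-subgroup p-values and no test of whether the effect differs between subgroups, so rows can appear to differ through chance or low power

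*SAP*

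**What the plan says.** Table 2c (SAP Appendix A) breaks the primary endpoint down "by age, sex, and CHADS-VASC score in the modified intention to treat (mITT) analysis". The rows are female and male; ages up to 64, 65–74, 75–84 and 85 or over; and CHA2DS2-VASc 2–3, 4–5 and 6 or more. Each row gives n/N, the unadjusted and adjusted parameter estimates with standard errors, both odds ratios with 95% confidence intervals, and one p-value for the adjusted odds ratio. There is no interaction column.

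SAP II states for the whole plan: "All tests will be two-sided and a p-value of <0.05 will be considered statistically significant. No multiplicity adjustment will be made".

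The primary model in SAP II.C.1 contains treatment and baseline covariates but no treatment-by-covariate term. SAP II.C refers to Tables 2a–c without giving a subgroup method or a rule for reading the rows. The only heterogeneity to be assessed is across Data Partners (SAP II.A). The protocol has no subgroup objective by age, sex or score.

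By contrast, SAP I.B marks the possible split by warfarin and novel OAC as descriptive, with no formal testing. Table 2c has no such label.

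**The concern.** A row's p-value asks whether the odds ratio in that row differs from 1. A subgroup table prompts another question: do the odds ratios differ from each other? The plan has no test for that. A reader is left to compare significant rows with non-significant ones, which is not a valid test of heterogeneity and has no controlled error rate.

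What is at stake is a false claim that the mailing works in some age groups and not in others. The risk is greatest when the true effect is modest. The trial as a whole can then be clearly positive while individual rows have only moderate power.

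**Working it through.** **Inputs from the documents.** "33% OAC initiation rate in the delayed intervention arm"; "38% OAC initiation rate in the early intervention arm"; "1-year attrition rate: 30% dropout or lost-to-follow-up"; about 80,000 patients randomized 1:1; two-sided 0.05.

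**Reproducing the plan's own figures.** The protocol names the method as "OAC Initiation Endpoint (33% Control Rate), continuity corrected Chi-square". For 33% vs 38% this gives 1,963, 2,418 and 3,401 per arm at 90%, 95% and 99% power. Dividing by 0.70 and rounding up gives 2,805, 3,455 and 4,859, exactly the stated table. The SAP's summary, "Roughly 10,000 patients who meet the inclusion/exclusion criteria will yield more than 99% power to detect a 5% absolute difference", agrees.

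**Evaluable base.** 80,000 × 0.70 / 2 = 28,000 per arm. The same base reproduces the stated stroke/TIA power:
- Control rate: 0.33 × 7% + 0.67 × 18% = 14.37%.
- Against 13.82% the power is 46.4% (stated 46%).
- Against 13.545% the power is 80.4% (stated 80%).

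**Assumed, because the documents do not say.** Age shares of 20/30/30/20% or 10/35/35/20%; sex 50/50; score 35/45/20%; a 33% control rate and the same absolute effect d in every row.

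**Row power.** With n = 28,000 × share per arm, power = Φ[(d − 1.96·se0)/se1], where se0 = √(2p̄(1−p̄)/n) and se1 = √((p1(1−p1)+p2(1−p2))/n).

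Example: d = 1.5 points and share 20%, so n = 5,600 and p̄ = 0.3375. Then se0 = 0.00894, se1 = 0.00894, and (0.015 − 0.01752)/0.00894 = −0.28, so power is 39%. For shares 20/30/30/20% the row powers are 39/54/54/39%, while overall power is 96%.

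**Chance of mixed rows.** Rows within a factor hold different patients, so P(mixed) = 1 − Π(power) − Π(1 − power). At 1.5 points with shares 20/30/30/20% this is 1 − 0.044 − 0.080 = 0.877.

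| Common effect | Age 20/30/30/20 | Age 10/35/35/20 | Sex 50/50 | Score 35/45/20 |
|---|---|---|---|---|
| 1 point | 66% | 67% | 49% | 64% |
| 1.5 points | 88% | 89% | 37% | 76% |
| 2 points | 77% | 84% | 11% | 53% |
| 3 points | 19% | 41% | 0.1% | 9% |
| 5 points (planned) | 0.04% | 2.6% | <0.1% | <0.1% |

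Binomial simulation (100,000 runs; 1, 2, 3 and 5 points; the 10/35/35/20% age shares, sex and score) gives the same results within rounding.

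**No effect anywhere.** With nine independent tests, P(at least one p<0.05) = 1 − 0.95⁹ = 37%. When the three factors split the same patients, simulation gives 32%.

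**A heterogeneity test instead.** Cochran's Q on the row log odds ratios, with 1 df for sex, 3 for age and 2 for score, rejected in 4.9–5.1% of simulated trials under a common effect, at every size and effect tried. Over three independent tests the chance of any false signal is 1 − 0.95³ = 14%.

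**The case against.** A reader might infer that subgroups will look different because of their size alone. The documents do not support that.

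- At the effect the trial is planned for, nearly every row would be significant, and mixed rows occur in under 3% of trials for any factor.
- Size changes precision and hence the p-value. It does not change the expected odds ratio. Two equal halves by sex would still disagree 49% of the time at a 1-point effect, through low power and chance.
- The 88–89% figure is close to the worst case in the range shown, and it belongs to age, the factor with the most rows.

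It is also fair to say that no passage announces claims of differential effect, that Table 2c shows n/N, odds ratios and intervals so that overlap is visible, and that the primary estimate is untouched. A heterogeneity test could also be computed later from the planned outputs.

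These points limit the size of the problem but do not remove it. The 5-point effect is a planning assumption, and Protocol X says there is no current evidence that insurer communications change anticoagulant use, so a smaller effect is realistic. At 1.5 points the trial keeps 96% power overall while the age rows will usually be mixed. The p<0.05 rule covers all tests, and the table is not marked as descriptive.

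**Conclusion.** The point holds in a limited form. The plan tests each of nine rows against an odds ratio of 1 and never tests whether the rows differ, so subgroups can appear to differ through chance or low row power when the effect is the same. How likely this is depends on the true effect: for age it is more likely than not at 1 to 2 points, an appreciable risk at 3, and slight at the planned 5. The figures rest on 28,000 evaluable patients per arm, which the plan's own numbers support, and on subgroup shares that are assumed. The gap in method does not depend on either. It is worth fixing because it is cheap. It does not threaten the primary analysis.

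**What to change.** Add to Table 2c one treatment-by-subgroup heterogeneity p-value per factor. The simplest route is Cochran's Q on the pooled adjusted log odds ratios and standard errors of that factor's rows. Each Data Partner already returns these estimates, so no new site models are needed. Site-level interaction terms pooled by inverse variance are an alternative, but they require extra models and new return items in the distributed programs.

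Keep the row odds ratios and 95% confidence intervals. Label the row p-values descriptive, or drop them. State in SAP II.C that any claim of a differential effect rests only on the heterogeneity test, and that a non-significant result does not prove the effects equal.

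The cost is three calculations at the coordinating level, one table column and a sentence or two of text. Q ignores any correlation between rows whose patients share a provider. SAP II expects few patients to share a provider, so this should be slight.

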# with ≥1 encounter			
Mean			
Standard deviation			
Minimum			
Maximum			
Median (range across sites)			
Outpatient/ambulatory encounters			
Total # of encounters per arm (N)			
# with ≥1 encounter			
Mean			
Standard deviation			
Minimum			
Maximum			
Median (range across sites)			
Days from follow up start to first outpatient/ambulatory encounter			
Total # of encounters per arm (N)			

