The complete code list for inclusion and exclusion criteria is accessible on the Sentinel website (https://www.sentinelinitiative.org/FDA-catalyst/projects/implementation-randomized-controlled-trial-improve-treatment-oral-anticoagulants-patients).

VIII. INTERVENTIONS

A. PATIENT-LEVEL INTERVENTIONS (EARLY INTERVENTION ARM)

- Letters to patients that (1) explain to the patient that he or she appears to have AF, characterize the risk of stroke, and emphasize that although there may be a medical reason, the patient does not seem to be on an anticoagulant and (2) encourage the patient to discuss this with his or her provider to ask if he or she might benefit from OAC therapy to prevent stroke.
- Written education materials about AF and anticoagulants, including answers to commonly asked questions
- Website with the patient-focused information contained in the letters to patients

B. PROVIDER-LEVEL INTERVENTIONS (EARLY INTERVENTION AND DELAYED INTERVENTION ARM)

- Letters to providers:
 - Early intervention letters to providers that explain this project, the nature of the problem, and identify a list of the provider's patients who have been contacted, as the provider and patient letters will be sent at approximately the same time; describe evidence and guidelines regarding oral anticoagulation
 - Delayed intervention letters to providers that explain this project, the nature of the problem, and identify a list of the provider's patients who are at risk for stroke and have not been treated with an oral anticoagulant; describe evidence and guidelines regarding oral anticoagulation
- Response mailer that gives the provider the opportunity to share the rationale for his or her patient(s) not being on OAC

- Web portal with access to clinical practice guidelines, decision support tools including from professional societies, podcasts, and case studies targeted at improving the appropriate use of OAC for AF
- Information sheet describing top misperceptions of barriers to OAC use
 - 1. Misperception of benefit and risk of aspirin: it is neither safe nor effective
 - 2. Misperception around risk of resuming OAC (months) after bleeding
 - 3. Misperception around risk of OAC regarding patients who fall
 - 4. Opportunities with NOACs for patients who have not tolerated warfarin
 - 5. Concern about lack of an antidote for the NOACs

IX. METHOD OF ASSIGNING PATIENTS TO AN INTERVENTION

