For each of these outcomes, time-to-event survival methodology will be implemented. Kaplan-Meier estimator¹² will be used to estimate the cumulative incidence rate during all follow-up and the log-rank test¹³ will be used to compare the survival curves. The Cox proportional hazards model with early intervention vs. delayed intervention as main effect will be used to model the time to event, after adjusting for baseline risk factors listed in Appendix A Table A. The hazard ratio, 95% CI and p-value will be presented to summarize the difference in the risk of clinical outcome between early intervention and delayed intervention groups. In-hospital death or medically attended death will be collected through claims data.

Each Data Partner will run SAS program(s) distributed by HPHCI, developed with the statistical team at Duke DCC, to perform analysis on their cohort of patients and return the results to HPHCI. For the comparison of cumulative incidence, each Data Partner will return the estimate of cumulative

occurrence and 95% CI by early intervention vs. delayed intervention, and p-value, as shown in Table 7 in Appendix A (there will be one for each Data Partner). For the comparison of risk, each Data Partner will return the parameter estimate (SE), hazard ratio, 95% CI and p-value, as shown in in Appendix A Table 8 (there will be one for each Data Partner). The statistical team will use meta-analysis methods to integrate the results and obtain the results for entire study population.

5. Health Care Utilization

The total counts of health care utilization (number of outpatient visits, emergency department visits, hospital admissions, and days hospitalized) at the end of follow-up time, including AF and non-AF related care, will be summarized by early intervention and delayed intervention group, as shown in Table 9 in Appendix A.

III. REFERENCES

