	Hospitalization for ischemic or hemorrhagic stroke or systemic embolism					
	Hospitalization for any bleeding					
	Composite of ischemic stroke, hemorrhagic stroke, systemic embolism and hospitalization for any bleeding					
	All-cause in-hospital death [PDX flag not applicable]					

Kaplan Meier curves will be generated for analyses related to Table 7.

Table 8. Hazard ratio of each outcome: early intervention vs. delayed intervention in the modified intention to treat (mITT) analysis

With / without Principal Discharge Diagnosis (PDX) Flag	Outcomes	Early Intervention, n/N (%)	Delayed Intervention, n/N (%)	Parameter Estimate (SE)	Unadj. Hazard Ratio (95% CI)	Adj. Hazard Ratio (95% CI)	p-value for adjusted HR
Principal Discharge Diagnosis (PDX Flag) Only	Hospitalization for ischemic stroke or unknown stroke						

	Hospitalization for TIA						
	Hospitalization for systemic embolism						
	Hospitalization for ischemic stroke, TIA, or systemic embolism						
	Hospitalization for hemorrhagic stroke						
	Hospitalization for ischemic or hemorrhagic stroke						
	Hospitalization for ischemic or hemorrhagic stroke or systemic embolism						
	Hospitalization for any bleeding						
	Composite of ischemic stroke, hemorrhagic stroke, systemic embolism and hospitaliz						

	ation for any bleeding						
Ignore Principal Discharge Diagnosis (PDX) Flag	Hospitalization for ischemic stroke or unknown stroke						
	Hospitalization for TIA						
	Hospitalization for systemic embolism						
	Hospitalization for ischemic stroke, TIA, or systemic embolism						
	Hospitalization for hemorrhagic stroke						
	Hospitalization for ischemic or hemorrhagic stroke						
	Hospitalization for ischemic or hemorrhagic stroke or systemic embolism						
	Hospitalization for any bleeding						

	Composite of ischemic stroke, hemorrhagic stroke, systemic embolism and hospitalization for any bleeding						
	All-cause in-hospital death						

Kaplan Meier curves will be generated for analyses related to Table 8.

Clinical endpoints for Table 8 will be based only on diagnoses that are the principal discharge diagnoses.

Table 9. Health care utilization during all follow up time: early Intervention vs. delayed Intervention in the modified intention to treat (mITT) analysis

	Early Intervention	Delayed Intervention	p-value
Total patients	N =	N =	NA
Total encounters			
Total # of encounters per arm (N)			NA

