# with ≥1 encounter			
Mean			
Standard deviation			
Minimum			

Maximum			
Median (range across sites)			
Emergency department encounters			
Total # of encounters per arm (N)			

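### SAP Table 9 gives days to first outpatient visit a p-value column but no rule for patients without a visit, so any test there compares visitors, not randomized arms

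*SAP*

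**What the plan says.** Table 9 is titled "Health care utilization during all follow up time: early Intervention vs. delayed Intervention in the modified intention to treat (mITT) analysis". Among its count blocks is one for a duration, "Days from follow up start to first outpatient/ambulatory encounter". That block reuses the rows of the count blocks: total encounters, the number "with ≥1 encounter", mean, SD, minimum, maximum and median. It has no row for censored patients, no Kaplan-Meier estimate and no hazard ratio.

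The table has a p-value column. It is marked NA for the total number of patients, the total number of encounters in the first block and the total days hospitalized. It is blank elsewhere, including this block.

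The only text on Table 9 is SAP II.D.5. It says that utilization counts "will be summarized by early intervention and delayed intervention group, as shown in" Table 9. It does not mention days to first visit, names no test and gives no rule for patients without a visit.

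Two general rules in SAP section II bear on the row. On censoring: "For the time-to-event analysis, patients will be censored from the analysis at the time of death, disenrollment from the health plan" (other reasons follow). On significance: "All tests will be two-sided and a p-value of <0.05 will be considered statistically significant", with no multiplicity adjustment.

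Time to first OAC fill has the same structure, and SAP II.D.1 and Table 3 give it Kaplan-Meier estimates and a Cox model.

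**The concern.** Days to first visit is a time-to-event variable laid out as if it were a count. A patient who never visits, or who is censored before visiting, has no number of days, and the SAP neither imputes one nor censors this row. No document states that the mean is limited to visitors, but the layout allows no other computation.

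The patient letter is meant to "encourage the patient to discuss this with his or her provider" (Protocol VIII.A), so whether a patient visits at all may depend on the arm. Visitors in the early arm then need not be comparable with visitors in the delayed arm, and randomization no longer protects the comparison. If the letter brings in people who would not otherwise have come, and they come later than regular attenders, the early-arm mean rises even though attendance improved.

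At stake is how one row of a secondary-endpoint table is read. In a trial of this size, a shift of about a day can reach p<0.05.

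**Working it through.** **1. Sample size.** The documents give no figure for this row, so I take the analysable number from the SAP's stroke/TIA power statement (SAP I.G.2): about 80,000 patients, 1:1, 30% attrition, hence 40,000 × 0.70 = 28,000 per arm. Check against the stated power:
- Delayed arm: 0.67 × 18% + 0.33 × 7% = 14.37%. Early arm at 38% OAC: 0.62 × 18% + 0.38 × 7% = 13.82%.
- SE = √[(0.1437 × 0.8563 + 0.1382 × 0.8618)/28,000] = 0.00294; z = 0.0055/0.00294 = 1.87; power = Φ(1.87 − 1.96) ≈ 46%, as stated.
- At 40.5% OAC the same steps give 80%, as stated.

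**2. Smallest mean difference that reaches p<0.05.** With 28,000 values per arm this is 1.96 × SD × √(2/28,000): 0.50 days for SD 30, 0.99 for SD 60 and 1.49 for SD 90. The SDs are assumptions.

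**3. Visitor-only mean.** All inputs here are assumptions. In the delayed arm 90% visit, at mean 40 days. In the early arm the same 90% visit at mean *m*, and an extra share *x* visits at mean *M*. The early-arm mean is (0.90*m* + *xM*)/(0.90 + *x*).

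| *m* | *x* | *M* | Early-arm mean | Difference from 40 |
|---|---|---|---|---|
| 40 | 0.02 | 120 | (36 + 2.4)/0.92 = 41.74 | +1.74 |
| 40 | 0.02 | 60 | (36 + 1.2)/0.92 = 40.43 | +0.43 |
| 40 | 0.02 | 20 | (36 + 0.4)/0.92 = 39.57 | −0.43 |
| 38 (5% sooner) | 0.02 | 120 | (34.2 + 2.4)/0.92 = 39.78 | −0.22 |
| 38 (5% sooner) | 0.05 | 120 | (34.2 + 6.0)/0.95 = 42.32 | +2.32 |

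In the first three rows no regular attender's visit moves and more patients are seen, yet the sign of the difference follows *M* alone.

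**4. Significance of the first row, taking exponential times.** There are 25,200 delayed and 25,760 early visitors.
- Delayed variance: 40² = 1,600. Early variance: (0.90 × 2 × 40² + 0.02 × 2 × 120²)/0.92 − 41.74² ≈ 2,014.
- SE = √(1,600/25,200 + 2,014/25,760) = 0.376; z = 1.74/0.376 ≈ 4.6.
- For a Wilcoxon test, the chance that an extra visitor comes later than a regular one is 120/160 = 0.75. The early-later probability is therefore (0.90 × 0.50 + 0.02 × 0.75)/0.92 = 0.5054. Its SE is √[(25,200 + 25,760)/(12 × 25,200 × 25,760)] = 0.00256, so z ≈ 2.1.

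**5. Simulation** (100 trials per scenario, 28,000 per arm, 365 days). In the first row, a visitor-only t-test showed a significant delay in 99% of trials and a Wilcoxon test in 94%. The Wilcoxon rate is sensitive to the assumed shape of visit times: z of 2.1 in step 4 implies a rate much nearer one half. In the other rows the t-test showed a delay in 29% (*M* = 60), 0% (*M* = 20), 1% (5% speed-up, *x* = 0.02) and 100% (5% speed-up, *x* = 0.05). With no extra visitors there was no excess of false delays.

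**6. All patients, with non-visitors censored.** If extra visitors are only added, early-arm cumulative incidence at day *t* is 0.90*F(t)* + 0.02*G(t)*, where *F* and *G* are the visit-time distributions of regular and extra visitors. This is never below the delayed arm's 0.90*F(t)*, so there is no delay to find. In the first-row simulation the log-rank test favoured earlier visits in 97% of trials and showed a delay in none.

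**The case against.** Most of the case on the other side concerns how far the point may be pushed, and much of it stands.

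- **No test is specified.** SAP II.D.5 speaks only of summarizing. Blank p-value cells also stand beside SDs, minima and maxima, so a blank cell does not prove a planned test. The total-encounters row, which has no meaning for a duration, suggests copied template rows. This stands: the p-value is an inference. The SAP does mark NA where it wants none, however, and has not done so here.
- **A reader might infer that this row is the SAP's only check on whether the letter works.** It is not. Table 9 also counts outpatient encounters and patients with at least one, and Tables 2b and 3 time OAC initiation. It is only the sole timing measure of outpatient visits, which cover AF and non-AF care alike.
- **The higher attendance is visible in the same table.** At 92% against 90% of 28,000, z = 0.02/√[(0.90 × 0.10 + 0.92 × 0.08)/28,000] ≈ 8 in favour of the letter. A careful reader would see it. It helps interpretation but does not repair the p-value.
- **The direction is assumed.** Nothing in the documents says that extra visitors come late. This stands, and the table in the working shows both signs.
- **Varying follow-up might be thought a separate bias.** Both arms start on the same wave dates within each Data Partner (SAP I.F), so differing duration is largely common to them. The documents do not support more than that.

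**Conclusion.** The point holds as a gap in one row of a secondary utilization table. As laid out, days to first outpatient visit can only be computed among patients with a visit, and a between-arm test on it is not a randomized comparison. That conclusion needs no numbers. It rests on the layout of Table 9 and the absence of any rule for patients without a visit.

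The size and sign of the bias cannot be stated. Under the assumed inputs, 2 extra percentage points of visitors move the visitor-only mean by −0.4 to +1.7 days as their mean visit time runs from 20 to 120 days. A 5% speed-up among regular attenders removes the false delay with 2 extra points but not with 5.

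A reader might go further and conclude that the trial will report a beneficial letter as a delay. The documents do not support this: it needs extra visitors who come later than regular ones, no sufficient speed-up among the rest, and a test that the SAP text does not name. The primary endpoint, the other OAC analyses and the clinical outcomes are untouched.

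**What to change.** Analyse time to first outpatient encounter in all mITT patients, from the mailing or pseudo-mailing date, with the censoring rules already in SAP section II. Report Kaplan-Meier cumulative incidence of a first visit by arm, for example at 42, 90 and 183 days (the Table 2b windows) and at 365 days. If a test is wanted, use the pooled hazard ratio from the Table 3 program.

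Keep the visitor-only mean and median as descriptive, label them as restricted to patients "with ≥1 encounter", and set their p-value to NA. Add a sentence to SAP II.D.5 that names the variable and its handling, and drop the total-encounters row from this block. The least that would do is the label and the NA.

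The row already needs the first-visit date, so no new data are required. The cost is a little extra programming and output at each Data Partner for a secondary table. A hazard ratio would add one more test to a plan without multiplicity adjustment, which is a reason to leave it optional.
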